10 CLINICAL MONITORING

10.1 Site Monitoring Plan

Site monitoring is conducted to ensure that the human subject protections, study and laboratory procedures, study intervention administration, and data collection processes are of high quality and meet sponsor, ICH/GCP guidelines and applicable regulations, and that this trial is conducted in accordance with the protocol, protocol-specific MOP and applicable sponsor standard operating procedures. DMID, the sponsoring agency, or its designee will conduct site-monitoring visits as detailed in the clinical monitoring plan.

Site visits will be made at standard intervals as defined by DMID and may be made more frequently as directed by DMID. Monitoring visits will include, but are not limited to, review of regulatory files, accountability records, CRFs, source data (paper and electronic), audit trails, ICFs, medical and laboratory reports, and protocol and GCP compliance. Site monitors will have access to the study site, study personnel, and all study documentation according to the DMID-approved site monitoring plan. Study monitors will meet with site principal investigators to discuss any problems and actions to be taken and document visit findings and discussions.

11 STATISTICAL CONSIDERATIONS

11.1 Study Hypotheses

A formal hypothesis test is planned to compare nitazoxanide to placebo with respect to the primary efficacy outcome measure. The time from randomization until clinical resolution of Norovirus for at least 48 hours through 180 days will be compared between the two study arms.

The null hypothesis is that there is no difference in time until clinical resolution between study arms, with a two-sided alternative. The test for primary efficacy hypothesis will be conducted using a Log-Rank test at the 5% two-sided level of significance.

11.2 Sample Size Considerations

Sample size calculations assume a 50% reduction in the median duration of diarrhea for the nitazoxanide-treated group compared to those receiving placebo. The median diarrhea duration for the placebo group is assumed to be 135 days, while the median diarrhea duration for the treatment group is assumed to be 67.5 days. Given these assumptions, a sample size of 64 subjects in each arm (128 total) is required to achieve 90% power using the Log-Rank test. Accounting for a 20% attrition rate, final sample size will be 80 in each arm (160 total).

Though discouraged, the protocol allows for subjects in either study group to receive additional nitazoxanide after 28 days. Under the assumptions of treatment efficacy, additional treatment received by placebo subjects would reduce the median duration of symptoms for the placebo group to be closer to that of the nitazoxanide-treated group. It is assumed that subjects who would have the worst study outcomes (longest time to clinical resolution of diarrhea) will be the most likely to receive additional treatment. Subjects receiving additional treatment will be imputed as having the worst outcome (time to resolution censored at 180 days). Accounting for this imputation method, the power attained for the primary comparison was computed via simulation (R version 3.0.3). Estimated power is displayed in the following table, varying the proportion of subjects in each study group who receive additional treatment

		Proportion Receiving Additional Treatment in the Placebo Group						
		0%	5%	10%	15%	20%	25%	30%
Proportion re-treated in the nitazoxanide Group	0%	91.3%	91.6%	91.7%	91.6%	91.8%	92.0%	92.3%
	5%	91.4%	91.5%	91.6%	91.2%	91.2%	91.8%	92.5%
	10%	-	91.5%	92.0%	91.2%	91.8%	91.2%	92.2%
	15%	-	-	90.7%	90.7%	91.0%	91.6%	91.8%
	20%	-	-	-	87.3%	87.1%	87.0%	87.7%
	25%	-	-	-	-	74.0%	73.9%	75.2%
	30%	-	-	-	-	-	40.0%	40.9%

For example, if 15% of placebo subjects receive nitazoxanide, and 5-10% of subjects in the nitazoxanide-treated group receive additional treatment, the power is estimated to be 91.2%. Note that implausible scenarios (where substantially more nitazoxanide subjects receive additional treatment than do placebo subjects) have been omitted from the table.

11.3 Planned Interim Analyses

11.3.1 Safety Review

As described in Section 9.6, the DSMB will meet and review safety data at regular enrollment milestones. The study will be monitored to determine if any of the safety halting rules described in Section 9.5 is met. The halting rules do not utilize any statistical criteria and no formal hypothesis testing is planned to occur for the safety reviews.

11.3.2 Efficacy Review

The DSMB will review available clinical and virologic efficacy data, however no formal hypothesis testing is planned.

11.4 Final Analysis Plan

11.4.1 General Principles

The SDCC will perform all analyses after final data lock. Tabulations will be used extensively to summarize the data. Summary statistics displayed for continuous data will include measures of central tendency such as the mean or median, and measures of dispersion such as the standard deviation or inter-quartile range. Summary statistics for discrete data will include absolute and relative frequencies and confidence intervals where appropriate.

In presenting statistical inferences, the statistical claim (i.e. null and alternative hypotheses) will be clearly stated, the method used for hypothesis testing will be described and appropriately referenced, and the assumptions underlying the methods will be validated.

More details of the analyses to be performed will be included in a separate Statistical Analysis Plan.

11.4.2 Analysis Populations

The safety population (grouped by actual treatment received) will include all subjects who are randomized, have received at least one dose of study treatment and have at least one safety assessment.

The modified intent-to-treat (mITT) population includes all randomized subjects who received at least one dose of assigned study drug. Analyses are performed according to randomized treatment assignment, not the treatment received.

The per-protocol (PP) population will include all subjects who met all inclusion/exclusion criteria, complied with the assigned study product, complied with the daily diary, and were followed up until resolution of symptoms, or completed 180 days without resolution of symptoms.

A subject is considered to be compliant with the assigned study product if he/she takes at least 75% of the scheduled doses through 28 days, and does not receive additional nitazoxanide before their primary outcome is observed.

A subject is considered to be compliant with the daily diary if he/she is missing no more than 1.5/7 days per week over the 8 weeks.

11.4.3 Efficacy Analyses

11.4.3.1 Analysis of Primary Outcome Measure

The primary efficacy outcome measure is the time from randomization to initial clinical resolution of Norovirus for at least 48 hours, assessed through 180 days, in each study arm. Clinical resolution will be assessed from the daily diary by the subject and will be defined as:

- a. Cessation of vomiting and
- b. No stools classified by the Bristol Stool Chart as diarrhea (Type 6 or 7)

The primary efficacy outcome measure will be assessed in the mITT population. Subjects who receive additional treatment with nitazoxanide other than their assigned study product will be considered censored at 180 days. To assess the effect of the choice of analysis population and additional treatment, the analysis will be repeated as a secondary analysis in the PP population. Sensitivity analyses may be performed to further assess the effect of additional treatment. The details of any sensitivity analyses will be detailed in the Statistical Analysis Plan.

The null hypothesis that the time to first clinical resolution of Norovirus is the same in both treatment arms will be tested using a stratified Log-Rank test to take into account the stratification at randomization. Estimates for median time to resolution and corresponding 95% confidence intervals will be reported for each treatment arm.

We will consider 80% compliance across the monitoring period acceptable [missing no more than 1.5/7 days per week over an 8 week period]. While we will not exclude patients, who are below this compliance for any monitoring period, we will conduct a sensitivity analysis comparing those with few missing values to those with 2 or more missing values per week.

With respect to missing data for the primary endpoint, the primary analysis will be handled as follows:

- Data that are missing after a subject has reached clinical resolution will not affect the primary time to event analysis and therefore will be ignored
- Subjects who drop out, are lost to follow-up, withdraw consent, or otherwise stop completing daily diary entries before clinical resolution will be censored on the day of their last completed diary
- Subjects with a gap in outcome data prior to clinical resolution will be handled depending on their last completed diary entry and their next completed diary entry:
 - If the last completed diary entry and the next completed diary entry have the same outcome (i.e., they are still symptomatic on both days or they have no symptoms on both days), then the gap will be imputed with the same outcome
 - If this imputation results in the subject being defined as having clinical resolution during this gap, their time to resolution will be the median of the interval
- If the last completed diary entry and the next completed diary entry have different outcomes (i.e., the last one is symptomatic and the next one is asymptomatic, or vice versa), then the gap will be imputed with a symptomatic outcome (no resolution)

The above method will be considered primary and additional methods such as worst case scenario or best case scenario may be explored as supportive analyses to assess robustness of results.

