3.3. Study Definitions and Derived Variables

Diarrhea:

Diarrhea will be defined as Type 6 or 7 on the Bristol Stool chart.

Baseline Value:

The baseline value will be defined as the last value obtained prior to the first dose of study product unless otherwise noted.

Additional Nitazoxanide:

Any nitazoxanide reported as a concomitant medication will be considered additional nitazoxanide.

Initial Clinical Resolution of Norovirus Symptoms:

Clinical resolution of Norovirus symptoms will be assessed from the daily diary by the subject and will be defined as:

- Cessation of vomiting and,
- No stools classified by the Bristol Stool Chart as diarrhea (Type 6 or 7).

Subjects will need to have at least two consecutive daily diary entries where they reported no vomiting, no Bristol Stool Type 6, and no Bristol Stool Type 7 to meet the criteria for initial clinical resolution. There are several variables in the daily diary that indicate whether the subject had diarrhea or vomiting for that day.

Daily Diary Diarrhea Questions:

- Phase 1 (Treatment Phase):
 - Number of Bristol Type 6 stools? (Quantitative)
 - Were there too many Bristol Type 6 stools to count? (Qualitative)
 - Number of Bristol Type 7 stools? (Quantitative)
 - Were there too many Bristol Type 7 stools to count? (Qualitative)
- Phase 2 (Longitudinal Phase):
 - Did you have diarrhea today? (By diarrhea, we mean at least ONE bowel movement that could be described as Type 6 or 7.) (Qualitative)

Daily Diary Vomiting Questions:

- Phase 1 (Treatment Phase):
 - Did you have to take another dose because you threw up the first dose within 1 hour? (Qualitative)
 - How many times did you vomit today? (Quantitative)
- Phase 2 (Longitudinal Phase):
 - Did you vomit today? (Qualitative)

For a day to count towards clinical resolution during the treatment phase, the following responses must be recorded in the daily diary entry:

- Both quantitative diarrhea questions must be 0

- Both qualitative diarrhea questions must be missing (i.e. not “yes”)
- The quantitative vomiting questions must be 0
- The qualitative vomiting question must be “no”

For a day to count towards clinical resolution during the longitudinal phase, the following responses must be recorded in the daily diary entry:

- The qualitative diarrhea question must be “no”
- The quantitative vomiting question must be 0

If a daily diary entry is missing, refer to the imputation rules in Section [6.5](#).

Viral Load:

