5. SAMPLE SIZE CONSIDERATIONS

Sample size calculations assume a 50% reduction in the median duration of diarrhea for the nitazoxanide-treated group compared to those receiving placebo. The median diarrhea duration for the placebo group is assumed to be 135 days, while the median diarrhea duration for the treatment group is assumed to be 67.5 days. Given these assumptions, a sample size of 64 subjects in each arm (128 total) is required to achieve 90% power using the Log-Rank test. Accounting for a 20% attrition rate, final sample size will be 80 in each arm (160 total).

Though discouraged, the protocol allows for subjects in either study group to receive additional nitazoxanide after 28 days. Under the assumptions of treatment efficacy, additional treatment received by placebo subjects would reduce the median duration of symptoms for the placebo group to be closer to that of the nitazoxanide-treated group. It is assumed that subjects who would have the worst study outcomes (longest time to clinical resolution of diarrhea) will be the most likely to receive additional treatment. Subjects receiving additional treatment will be imputed as having the worst outcome (time to resolution censored at 180 days). Accounting for this imputation method, the power attained for the primary comparison was computed via simulation (R version 3.0.3). Estimated power is displayed in [Table 2](#), varying the proportion of subjects in each study group who receive additional treatment.

For example, if 15% of placebo subjects receive nitazoxanide, and 5-10% of subjects in the nitazoxanide-treated group receive additional treatment, the power is estimated to be 91.2%. Note that implausible scenarios (where substantially more nitazoxanide subjects receive additional treatment than do placebo subjects) have been omitted from the table.

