6.5. Missing Data

All attempts were made to collect all data per protocol. Imputations will only be performed for missing daily diary data as it relates to the primary endpoint. Missing daily diary data for the primary endpoint will be handled as follows:

- Data that are missing after a subject has reached clinical resolution will not affect the primary time to event analysis and therefore will be ignored
- Subjects who drop out, are lost to follow-up, withdraw consent, or otherwise stop completing daily diary entries before clinical resolution will be censored on the day of their last completed diary
- Subjects with a gap in outcome data prior to clinical resolution will be handled depending on their last completed diary entry and their next completed diary entry:
 - If the last completed diary entry and the next completed diary entry have the same outcome (i.e., they are still symptomatic on both days or they have no symptoms on both days), then the gap will be imputed with the same outcome
 - If this imputation results in the subject being defined as having clinical resolution during this gap, their time to resolution will be the median of the interval
 - If the last completed diary entry and the next completed diary entry have different outcomes (i.e., the last one is symptomatic and the next one is asymptomatic, or vice versa), then the gap will be imputed with the symptomatic outcome (no resolution).

[Table 3](#) provides summary statistics (n, mean, median, standard deviation, minimum, and maximum) of the number of imputed diary days per subject given the above imputation rules and the number of overall missing diary days per subject. The above method will be considered the primary imputation method for the primary endpoint. In addition, a sensitivity analysis on the primary endpoint will be conducted using worst case scenario for subjects who drop out, are lost to follow-up, withdraw consent, or otherwise stop completing

daily diary entries before clinical resolution. These subjects will be censored at 180 days (i.e., assuming resolution of symptoms occurred after Day 180). [Listing 9](#) provides subject-level details for the number of diaries missed by week.

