8.1. Primary Efficacy Analysis

The primary efficacy outcome measure is the time from randomization to initial clinical resolution of Norovirus for at least 48 hours, assessed through 180 days, in each study arm. Clinical resolution will be assessed from the daily diary by the subject and will be defined as in Section [3.3](#).

The protocol calls for a formal hypothesis test to compare nitazoxanide to placebo. The null hypothesis is that there is no difference in time until clinical resolution between study arms, with a two-sided alternative. A stratified Log-Rank test at the 5% two-sided level of significance was planned to test the hypothesis, however, due to early closure of the study, the number of subjects is too small to use a Log-Rank test. Instead, a stratified Cox proportional hazards model will be used to compare treatment to control through Day 180 with respect to time to clinical resolution. Stratification is based on acute versus chronic symptoms at baseline. No pediatric subjects were enrolled in the study and only one hematopoietic stem cell transplant subject was enrolled in the study; therefore, the transplant type and age range strata will not be included in the final analysis.

The primary analysis will be performed in the mITT analysis population. Missing diary data will be imputed using the methods described in Section [6.5](#). The treatment hazard ratio estimate, 95% confidence interval and p-value from the likelihood ratio test will be presented ([Table 16](#)). The median time to clinical resolution and 95% confidence interval will be summarized by treatment arm and duration of symptoms. In addition, stratum-specific estimates of the treatment hazard ratio within each duration of symptoms strata will be presented. Kaplan-Meier curves for each treatment arm will be displayed in [Figure 3](#). [Figure 6](#) will present Kaplan-Meier curves for each treatment arm and duration of symptoms strata.

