9.2. Measurements of Treatment Compliance

The number of subjects who received any treatment and the number of subjects who received all scheduled treatments through Days 7, 14, 21, and 28 is presented by treatment group in [Table 6](#). The number of subjects that received any additional nitazoxanide and additional nitazoxanide after Day 28 will also be included in the table. A subject is considered compliant with the assigned study product if they take at least 75% of the scheduled doses through 28 days and do not receive additional nitazoxanide before the primary outcome is observed. [Table 10](#) provides the number of subjects compliant with study product, the mean cumulative number of pills taken and the mean percentage of pills taken for each treatment group at Days 7, 14, 21, and 28. A listing of treatment compliance by subject is presented in [Listing 8](#).

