14.2. Changes in Planned Analyses

It was originally planned that the study would enroll 160 subjects allowing for larger sample statistical methods to be used; however, due to early closure of the study only 31 subjects enrolled. Therefore, it is anticipated that many of these tests will no longer be valid. Many of the analyses from the protocol have been updated to employ small sample techniques and will be primarily descriptive.

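### The documents conflict on how re-treated subjects enter the primary analysis, and the protocol's rule has no timing condition, so the primary hazard ratio is not uniquely defined

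*Protocol*

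**What the plan says.** Two places set a rule for subjects who take nitazoxanide beyond their assigned product:

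- Protocol 11.4.3.1, for the mITT primary analysis: "Subjects who receive additional treatment with nitazoxanide other than their assigned study product will be considered censored at 180 days".
- SAP Section 5, which treats the same handling as an imputation: "Subjects receiving additional treatment will be imputed as having the worst outcome (time to resolution censored at 180 days".

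The sections that define the analysis do not carry it:

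- SAP 3.3 defines the exposure, "Any nitazoxanide reported as a concomitant medication will be considered additional nitazoxanide", but attaches no consequence for the primary endpoint. Resolution there depends on diary entries alone.
- SAP 6.5 states: "Imputations will only be performed for missing daily diary data as it relates to the primary endpoint". None of the rules that follow concerns re-treatment.
- SAP 8.1 adds only: "Missing diary data will be imputed using the methods described in Section" 6.5. It does announce its other departures from the protocol, namely log-rank replaced by Cox and two strata dropped.
- SAP 14.2 is general: "Many of the analyses from the protocol have been updated to employ small sample techniques and will be primarily descriptive".

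A timing condition appears only for the per-protocol population. Protocol 11.4.2 requires that the subject "does not receive additional nitazoxanide before their primary outcome is observed", and SAP 6.3.2 and 9.2 repeat this. SAP 6.4 and Table 18 exclude every re-treated subject, whatever the timing, as a sensitivity analysis.

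**The concern.** There are two separate defects.

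First, the rule is stated in one part of the plan and shut out in another. Under SAP 3.3, 6.5 and 8.1, a placebo subject who resolves after open-label nitazoxanide is a placebo resolution. Under Protocol 11.4.3.1 and SAP Section 5, that subject is censored at Day 180. Using the diaries as observed is a coherent choice, but the protocol did not declare it and the SAP does not declare a change.

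Second, the endpoint is time to *initial* resolution, and the protocol allows nitazoxanide after Day 28 in defined circumstances, so it can follow a resolution. The censoring rule has no timing condition. Taken literally, it replaces an event already observed with a Day-180 censoring.

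At stake are the hazard ratio, confidence interval and p-value in Table 16. If the point stays open, the coding could be chosen after treatment assignments are known.

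**Working it through.** **1. How each text codes two subjects.** Subject P is on placebo, is re-treated at Day 60 while unresolved, and has clear diaries from Day 80. Subject N resolves on Day 10, relapses, and is re-treated on Day 90.

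| Text followed | P | N |
|---|---|---|
| Protocol 11.4.3.1 or SAP 5, literal | censored, Day 180 | censored, Day 180 |
| SAP 3.3 + 6.5 + 8.1 | event, about Day 80 | event, Day 10 |
| Protocol rule with the PP timing condition | censored, Day 180 | event, Day 10 |
| PP population | removed | kept, if otherwise compliant |
| Table 18 exclusion | removed | removed |

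The first three rows give three different primary analyses. The last two only remove subjects, so they cannot settle which coding applies in mITT.

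**2. The plan's own figures reproduce.** Inputs (Protocol 11.2, SAP 5): medians 135 and 67.5 days, 180-day follow-up, 64 per arm, 20% attrition.

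- Exponential hazard ratio for resolution: 135/67.5 = 2.0.
- P(resolved by Day 180) = 1 − 2^(−180/median): 0.603 on placebo, 0.843 on nitazoxanide, mean 0.723.
- Schoenfeld: 4(1.960 + 1.282)²/(ln 2)² gives 88 events, or 61 per arm. Freedman gives 95 events, or 66 per arm. Lachin-Foulkes gives 65 per arm. The stated 64 lies among these, and 64/0.8 = 80.
- Power table: log-rank simulation, 64 per arm, the slowest subjects in each arm censored at Day 180. Simulated versus stated (placebo/nitazoxanide re-treated): 0/0 91.4 v 91.3; 15/5 91.8 v 91.2; 20/20 87.1 v 87.1; 30/30 40.7 v 40.9.

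**3. What that table does not test.** It assumes the re-treated are the slowest resolvers. About 1 − 0.603 = 40% of placebo and 1 − 0.843 = 16% of nitazoxanide subjects are unresolved at Day 180 anyway. Up to those rates the rule only relabels subjects already censored. If re-treatment is unrelated to outcome, so that observed resolutions are overwritten, power at 15/15 is 77.0% (stated 90.7%) and at 20/20 is 70.3% (stated 87.1%).

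**4. Large-sample hazard ratio.** Simulated Cox model, 400,000 per arm, true value 2.0. Rates are assumed shares of each arm (placebo/nitazoxanide). Re-treatment starts between Day 28 and Day 90 in subjects still unresolved. With the rule omitted, the event falls at the earlier of natural resolution and re-treatment start plus an exponential time.

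| Handling | 15%/5% | 20%/10% | 30%/10% |
|---|---|---|---|
| Omitted, slowest re-treated, 67.5-day median after re-treatment | 1.76 | 1.79 | 1.56 |
| Omitted, random unresolved, 67.5-day median | 1.81 | 1.79 | 1.64 |
| Omitted, slowest re-treated, 135-day median | 1.85 | 1.86 | 1.70 |
| Applied, slowest re-treated | 2.00 | 2.00 | 2.00 |
| Applied, random unresolved | 2.13 | 2.05 | 2.29 |

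Literal rule, erasing resolutions before Day 150 in an assumed share of resolvers (placebo/nitazoxanide): 10%/10% gives 1.86, 5%/15% gives 1.56, 15%/5% gives 2.22. The shift can go either way.

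**5. At 31 subjects.** Assumed split 16/15, 20,000 replicates, median ratio of the hazard ratio after recoding to that before:

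| Recoding | One subject | Two subjects |
|---|---|---|
| Resolved nitazoxanide subject becomes censored | ×0.83 | ×0.71 |
| Resolved placebo subject becomes censored | ×1.20 | ×1.45 |
| Unresolved re-treated placebo subject, rule omitted versus applied | ×0.89 | ×0.83 (5–95% range 0.70–1.00) |

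Stratifying by acute/chronic symptoms, with 4 or 8 acute subjects assumed, changes these medians by no more than 0.01.

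**The case against.** The best reply is that the SAP supplements the protocol, so a rule it does not withdraw still stands. On that reading, the 'only' in 6.5 sits under a missing-data heading and concerns missing values; a re-treated subject's diary is not missing. The SAP also imputes viral loads and immunoglobulin values elsewhere, so 'only' cannot be global. This does not remove the conflict. SAP Section 5 calls Day-180 censoring for re-treatment an imputation, and SAP 8.1.1 uses the same word for Day-180 censoring of dropouts. The laboratory imputations do not concern the primary endpoint. If the rule does carry over, its missing timing condition carries over too.

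A sensible reader might supply that condition from the word 'initial' and from the PP definition. That is probably what was meant, but the sentence does not say it.

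The points on size have weight. No re-treatment counts are given. The 5%/15% case has more re-treatment on nitazoxanide than on placebo, a pattern Protocol 11.2 considers implausible; the 10%/10% case does not, and still gives 1.86. With about 31 × 0.723 = 22 events, the 95% interval is roughly the estimate multiplied or divided by exp(1.96 × 2/√22) ≈ 2.3, so recoding one subject is small beside sampling error. It is nevertheless an avoidable difference in the reported primary result, and re-treatment listings do not decide which result is primary.

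**Conclusion.** The concern holds. The sections that define the primary analysis conflict with Protocol 11.4.3.1 and with SAP Section 5, and the protocol's rule, read literally, discards observed initial resolutions. The sample size and power table are not in error.

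The effect is nil if no subject was re-treated. Otherwise its size and direction depend on who was re-treated and when. Under the planning model and the assumed rates, omitting the rule pulls a true hazard ratio of 2.0 down to between 1.56 and 1.86, and the literal rule gives anything from 1.56 to 2.22. At 31 subjects, one or two recoded subjects typically multiply the estimate by between 0.71 and 1.45. Re-treatment rates, start times, time to resolution after re-treatment and the 16/15 split are assumptions. The textual finding needs none of them. Because this decides what counts as an event in the primary analysis, it should be settled before the comparison is run.

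**What to change.** Put one rule in SAP 3.3 and 8.1, for example:

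> A subject whose first additional nitazoxanide precedes initial clinical resolution is censored at Day 180; a subject who met initial clinical resolution before any additional nitazoxanide keeps the observed event day.

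Then:

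- Reword 'only' in SAP 6.5 so that it does not exclude this rule, and say which rule takes precedence when a subject re-treated before resolution also stops the diary (Day 180, or the last diary as 6.5 has it).
- Record in SAP 14.2 the timing clarification and any departure from Protocol 11.4.3.1.
- Keep the Table 18 exclusion, and add beside it a sensitivity analysis using all diary days as observed regardless of re-treatment. This matters because Day-180 censoring itself overstates the effect (2.05 to 2.29 above) if re-treatment falls on unresolved subjects at random.

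The cost is a few lines of text and one more block in Table 18. No new data are needed: re-treatment is on the concomitant medication form and in Listing 11, and for Table 6 SAP 9.2 already promises: "The number of subjects that received any additional nitazoxanide and additional nitazoxanide after Day 28 will also be included in the table". The change concerns analysis only and takes no position on when re-treatment should be given.
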